12.3 Sample Size Determination

A sample size of 75 subjects will have 80% power to detect a difference in means of 8.194, assuming a standard deviation of differences of 25, using a paired t-test with a 5% two-sided

significance level. To allow for dropouts of up to 25%, approximately 100 subjects will be treated.

12.4 Analysis Populations

Full Analysis Set (FAS): The FAS will consist of all subjects who receive at least 1 drop of study treatment.

Per Protocol (PP) Set: The PP Set will consist of all subjects in the FAS with no protocol deviations expected to affect efficacy outcomes.

12.5 Statistical Analysis

12.5.1 General Considerations

Summaries for continuous variables will include the sample size (n), mean, standard deviation, median, minimum, and maximum. Summaries for categorical variables will include frequencies and percentages. Missing safety data will not be imputed.

12.5.2 Primary Effectiveness Analyses

12.5.3 Safety Analyses

12.5.3.1 Adverse Events

The number and percent of subjects with specific treatment-emergent adverse events (TEAEs) and the total number of occurrences of each TEAE will be summarized for the FAS. The number of subjects will be tabulated by Medical Dictionary for Regulatory Activities (MedDRA) system organ class and preferred term within each system organ class.

12.5.3.2 Subject Demographics and Baseline Characteristics

Race, sex, and age groups will be presented using discrete summary statistics. Age will also be presented using continuous summary statistics. Medical history data will be presented in a listing.

12.5.3.3 Prior and Concomitant Medications

Concomitant medication use will be summarized using the number and percentage of subjects using each type of medication by drug class and preferred term. Ocular and non-ocular medications will be presented in separate tables. Prior medications will be included in a listing but not included in the concomitant medication summary.

12.5.3.4 Subject Disposition

Subject disposition will be summarized using number and percentage of subjects. The reasons for study discontinuation will also be summarized.

12.5.3.5 Treatment Adherence

Treatment adherence will be computed as the number of doses administered divided by the number of doses expected $\times 100\%$. Adherence will be summarized using continuous and categorical (less than 80%, 80% to 120%, greater than 120%) summary statistics by treatment group.

12.5.3.6 Treatment Exposure

Duration of treatment exposure will be defined as the total number of days from treatment initiation until last dose date, as recorded at Visit 1 and the study exit CRF page. Duration of exposure to study treatment will be calculated as:

Duration = date of last dose – date of treatment initiation + 1.

12.6 Additional Statistical Considerations

12.6.1 Handling of Missing Data

Unless otherwise specified in the statistical analysis plan, missing data will not be imputed.

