5.2 Endpoints

5.2.1 Efficacy

The primary efficacy endpoint is the mean change from baseline (CFB) in dry eye symptom severity at Visit 3 (Day 7 ± 1 day).

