6.1 Overall Study Design and Plan: Description

This single-arm, open-label, multicenter, prospective study will consist of 4 study visits in subjects with DED. Subjects who sign the informed consent form (ICF) at the Screening/Baseline Visit (Visit 1; Day 1) will be enrolled in the study and screened for eligibility to participate in the study. Subjects will be asked to complete an Early Outcomes Survey - Baseline Visit 1 (Pre-dosing) to obtain baseline data at the start of Visit 1, after Ocular Surface Disease Index Questionnaire administration. Following subjects' confirmation of eligibility and at least 15 minutes after the completion of Schirmer's test, site staff will instill the first dose of Miebo and dispense Miebo to subjects. Subjects will then complete 2 additional Early Outcomes Surveys - Baseline Visit 1 (Post-dosing) at 5 minutes and 1 hour post-dose.

Subjects will then commence at-home treatment with Miebo 4 times daily (QID) bilaterally and will continue this for approximately 14 days. At Visits 2, 3, and 4 (Days 3, 7, and 14, respectively), subjects will complete 1 Early Outcomes Survey - Follow-up Visit in the clinic at least 30 minutes and no longer than 4 hours post-dose.

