7.3.3 Subject Completion

For those subjects who are eligible and have consented to participate, Visit 4 will be the final visit to complete their participation.

A subject who has missed visits or is missing study measurements will remain in the study. Subjects who require further follow-up for an AE will be followed according to [Section 11.3.5](#).

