7.3.4 Subject Discontinuation

A subject MUST be discontinued prior to the final study visit for any of the following reasons:

- Voluntary withdrawal
- Death
- Investigator decision that it is not in the best medical interest of the subject to continue participation in the study

A subject MAY be discontinued (at the discretion of the Investigator, the Sponsor, and/or the Institutional Review Board [IRB]) prior to the final study visit for several reasons, including but not limited to:

- Serious adverse event (SAE) and/or AE occurring during the course of the study that precludes continued follow-up
- Noncompliance with required study procedures
- Occurrence of a relevant exclusion criterion

Prior to discontinuing a subject from the study, every effort should be made to contact the subject, schedule a final study visit, and obtain as much follow-up data as possible. Whenever possible, subjects who have discontinued study treatment should be followed through the last scheduled study visit. Ongoing AEs will be followed as described in [Section 11.3.5](#). Subject withdrawals will be documented clearly on the source document and applicable Case Report Form (CRF). Subjects who discontinue from the study should be seen for routinely scheduled visits according to the standard of care by the Investigator or their ophthalmologist.

Notification of subject withdrawals will be made immediately to the Sponsor.

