7.3.5 Lost to Follow-Up

Subjects who do not return for scheduled visits, as defined by the visit window, and cannot be contacted may be considered lost to follow-up. The Investigator will try at least twice to reach the subject by telephone and/or email and will send a follow-up letter by certified mail before

considering the subject lost to follow-up. All follow-up attempts will be documented and kept with the subject's source documentation, and the applicable CRFs will be completed. The date a subject will be considered lost to follow-up will be the date of the last completed visit.

Efforts shall be made to keep the number of subjects lost to follow-up to a minimum, below 10% of the number of subjects treated.

8 Treatment Plan

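### Does a no-imputation default, with no visible sensitivity analysis, leave the Day 7 primary estimate unprotected against missing scores?

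*Combined protocol and SAP*

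**What the plan says.** The primary endpoint (Section 5.2.1) is the mean change from baseline in dry eye symptom severity at Visit 3, Day 7. Section 12.2 tests two-sided whether that mean is zero.

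- **Missing data (12.6.1):** "Unless otherwise specified in the statistical analysis plan, missing data will not be imputed". Section 12.5.1 separately rules out imputation of safety data.
- **Analysis set (12.4):** "The FAS will consist of all subjects who receive at least 1 drop of study treatment". No post-baseline score is needed.
- **Sizing (12.3):** 75 subjects give 80% power for a mean difference of 8.194 with SD 25, by a two-sided 5% paired t-test. Then: "To allow for dropouts of up to 25%, approximately 100 subjects will be treated".
- **Retention:** Section 7.3.3 says "A subject who has missed visits or is missing study measurements will remain in the study"; Section 7.3.4 says "Whenever possible, subjects who have discontinued study treatment should be followed through the last scheduled study visit"; Section 7.3.5 says "Efforts shall be made to keep the number of subjects lost to follow-up to a minimum, below 10% of the number of subjects treated".
- **Data collection (6.1):** at Visits 2, 3 and 4 "subjects will complete 1 Early Outcomes Survey - Follow-up Visit in the clinic".

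The primary efficacy analysis is redacted in the synopsis, and no text is visible under Section 12.5.2. The paired t-test appears only in the sample-size text.

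**The concern.** A paired t-test without imputation uses only subjects who have both a baseline and a Day 7 score. If that is the primary analysis, treated subjects without a Day 7 score belong to the Full Analysis Set in name but contribute nothing to the estimate. Treating 100 to keep 75 protects power and does nothing about bias. The Per Protocol Set deals with deviations, not missing scores.

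A single-arm study has no control arm in which similar losses could offset these. If subjects who do poorly tend not to return, the mean improvement is overstated, and at high missingness the significance of the test could also be in doubt.

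**Working it through.** **Inputs.** From Section 12.3: difference 8.194, SD of differences 25, n = 75, two-sided 5%, dropout up to 25%, about 100 treated. From Section 7.3.5: loss to follow-up below 10%. Assumptions, not in the documents: improvement is coded positive, the observed mean equals 8.194 with SD 25, and 100 are treated. Let f be the fraction without a Day 7 score and m their mean improvement. The 5% rate is also assumed.

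**1. The plan's own figure.** With the noncentral t distribution, df = 74 and noncentrality (8.194/25) × √75, power is 80.0%. The stated figure reproduces. 75/(1 − 0.25) = 100, so the inflation is right. Power would be 86.8% with 90 pairs and 90.1% with 100.

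**2. Bias of the observed-pairs mean.** The all-treated mean is (1 − f) × 8.194 + f × m, so the overstatement is f × (8.194 − m). It is zero if the missing resemble the observed. With no change in the missing (m = 0):

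| f | Pairs | Overstatement | SE = 25/√pairs | Overstatement/SE |
|---|---|---|---|---|
| 5% | 95 | 0.05 × 8.194 = 0.41 | 2.565 | 0.16 |
| 10% | 90 | 0.10 × 8.194 = 0.82 | 2.635 | 0.31 |
| 25% | 75 | 0.25 × 8.194 = 2.05 | 2.887 | 0.71 |

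**3. Effect on the test.** A delta-adjusted analysis keeps the standard error at 25/√pairs and shifts the estimate. With m = 0:

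- 10% missing: 0.90 × 8.194 = 7.375; 7.375/2.635 = 2.80; p = 0.006.
- 25% missing: 0.75 × 8.194 = 6.146; 6.146/2.887 = 2.13; p = 0.037.

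The smallest significant mean is 5.236 with 90 pairs and 5.752 with 75. Solving (1 − f) × 8.194 + f × m for that value gives the mean at which significance is lost:

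- 10% missing: (5.236 − 7.375)/0.10, a worsening of about 21.4 points.
- 25% missing: (5.752 − 6.146)/0.25, a worsening of about 1.6 points.

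**4. Would an obvious addition help?** The simplest one is to set missing changes to zero and rerun the t-test. At 25% missing the estimate falls to 6.146, but the added zeros shrink the SD to √(0.75 × (25² + 8.194²) − 6.146²) = 21.9. Then t = 6.146/(21.9/√100) = 2.80 and p = 0.0061, against 0.0058 for the observed pairs. At 10% the p-values are 0.0026 and 0.0025. The test hardly moves, so this would reassure falsely.

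A repeated-measures model using Day 3 can help only subjects with a Day 3 score. It adds nothing for those with baseline alone, and it needs the severity item in the survey at each visit, which the redacted survey content does not let a reader confirm.

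**The case for a change.** The strongest opposing case is that the no-imputation default is unredacted and real, that no control arm protects the estimate, and that fixing one sensitivity analysis before data are seen costs little. At the plan's own 25% allowance, a worsening of only 1.6 points on average in the missing would take away significance. A simulation with assumed inputs points the same way. With a true mean of 8.19, correlation between Day 3 and Day 7 changes of 0.5 to 0.7, and log-odds of dropout rising 0.5 to 1.5 per SD of worse Day 3 change, the observed-pairs mean is 8.9 to 10.3 at 10% missing and 9.7 to 13.0 at 25%.

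The direction of the bias and the fragility at 25% stand. Three things limit them.

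- The 25% is a sizing ceiling with no time point attached. Day 7 is the midpoint of a 14-day study whose rules keep subjects in after missed visits and, where possible, after stopping treatment.
- The simulation's upper ends are harsh. A mean of 10.3 at 10% missing requires the missing to average (8.194 − 0.90 × 10.3)/0.10, a worsening of about 11 points. None of the dropout inputs comes from the documents.
- 8.194 is a detectable difference, not an expected effect. A larger observed effect would tolerate more.

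One caution in the other direction also stands. Loss to follow-up is narrower than a missing Day 7 score, because withdrawals and a missed Visit 3 also count. The 10% is therefore a guide, not a bound.

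**Conclusion.** No change follows. The concern needs two conditions: that the primary analysis is the paired t-test on observed pairs, and that neither the redacted text nor the SAP deals with missing Day 7 scores. Neither can be established from the visible text, and what is blacked out cannot be counted as left out. Section 12.6.1 leaves room for the SAP to specify a method. The separate sentence on safety data is consistent with efficacy being handled elsewhere, though it does not prove it.

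What remains is a detail that analysts would ordinarily settle in the SAP, and a fair question to the sponsor. At 10% missing, with no change in the missing and an observed mean of 8.194 (SD 25), the overstatement is 0.82 points, or 0.31 standard errors, and the conclusion holds unless the missing worsen by about 21 points on average. It would matter near 25% missing, where the overstatement is 2.05 points and the margin on significance is thin. Replacing the paired t-test with a repeated-measures model is partly a matter of preference, and zero-filling would leave the test almost unchanged.

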10.1.3 Visit 3: Day 7 ± 1 day

The following study measurements will be collected:

- Concomitant medication
- Adverse event query

- [REDACTED]
- Dosing diary review by dedicated team member

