10.1.5 Unscheduled Visit(s)

Additional visits may be scheduled, as necessary, to ensure the safety and well-being of subjects. All additional examinations should be fully documented in the source documents and on Unscheduled Visit CRFs, as appropriate. Visits intended to fulfill scheduled visit requirements that fall outside the designated scheduled visit window will be collected and transcribed to the appropriate visit CRF.

If a subject is seen for multiple visits during a given visit timeframe, the data from the visit that are intended to meet the protocol requirements for the scheduled visit will be captured on the visit CRF. Where such a determination cannot be made, the first visit within the scheduled visit interval will be used for completion of the protocol-required scheduled visit CRF. Data from any additional visits within a scheduled visit interval will be captured on an Unscheduled Visit CRF.

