16.1 Appendix A Study Flow Chart

Visit Procedure	Screening/Baseline Visit 1 Day 1 [1]	Visit 2 Day 3 (+1 day)	Visit 3 Day 7 (±1 day)	Visit 4 Day 14 (±2 days)
Informed consent/HIPAA	X			
Demographics	X			
Medical/Surgical history	X			
Urine pregnancy test (for female subjects of childbearing potential)	X			
Previous/Concomitant medication	X	X	X	X
AE query	X	X	X	X
VA [2]	X			X
TBUT [2]	X			
Total CFS score (NEI scale) [2]	X			
Meibomian gland assessment (MGD score) [2]	X			
Schirmer's test [2]	X			
Inclusion/Exclusion criteria	X			
Instillation of study treatment (by site staff)	X[3]			
Early OutcomesSurvey – Baseline Visit 1 (Post-dosing)	X [4]			
Dispensation of study treatment	X			
Dispensation of dosing diary	X			
Review of dosing diary		X	X	X
Collection of study treatment and dosing diary				X
Trial exit				X

AE, adverse event; CFS, corneal fluorescein staining; HIPAA, Health Information Portability and Accountability Act; MGD, meibomian gland dysfunction; NEI, National Eye Institute; [REDACTED]

Disease Index; TBUT, tear film break-up time; VA, visual acuity; VAS, visual analog scale.

[1] Should a subject fail to meet eligibility requirements on Screening, further baseline assessment will be halted.

[2] Assessment to be conducted in the order as depicted in the study flow chart, at applicable visits.

[3] Instillation of study treatment (by study staff) should occur at least 15 minutes after completion of Schirmer's test.

[figure not shown]
[figure not shown]
[4] Survey to be completed by subject at 5 minutes and 1 hour post-dose.

[5] Survey to be completed by subject in the clinic at least 30 minutes and no longer than 4 hours post-dose.

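### Does the post-dose survey window leave subjects who have stopped drops without a defined place in the Day 7 primary analysis?

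*Combined protocol and SAP*

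**What the plan says.** The primary endpoint is the mean change from baseline in dry eye symptom severity at Visit 3, Day 7 ± 1 (5.2.1).

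- **Survey timing.** Section 6.1 has the follow-up survey at Visits 2, 3 and 4 completed "in the clinic at least 30 minutes and no longer than 4 hours post-dose". Appendix A, footnote [5], repeats the rule: "Survey to be completed by subject in the clinic at least 30 minutes and no longer than 4 hours post-dose". Neither has wording for a subject who no longer doses.
- **Subjects who stop treatment.** Section 7.3.4 says that, where possible, "subjects who have discontinued study treatment should be followed through the last scheduled study visit", and asks sites to gather as much follow-up data as they can.
- **Missed measurements and deviations.** Section 7.3.3: "A subject who has missed visits or is missing study measurements will remain in the study". Section 8.4 keeps a subject's assessments going to the end of the study after a deviation, except where the subject is at risk or the subject's condition requires discontinuation. Under 10.1.5, scheduled visits that "fall outside the designated scheduled visit window will be collected and transcribed to the appropriate visit CRF".
- **Analysis sets.** The FAS is everyone who received at least one drop. The Per Protocol Set removes subjects with deviations expected to affect efficacy (12.4).
- **Missing data.** Section 12.6.1: "Unless otherwise specified in the statistical analysis plan, missing data will not be imputed".
- **Sample size.** Section 12.3 needs 75 subjects for a paired t-test. "To allow for dropouts of up to 25%, approximately 100 subjects will be" treated. Section 7.3.5 separately aims to keep loss to follow-up below 10%.

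The primary analysis is redacted in the synopsis, and under 12.5.2 only the heading can be read. The efficacy assessments in 11.1 and an item at Visit 3 (10.1.3) are also redacted.

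**The concern.** Two rules appear to collide. A subject who stopped drops on Day 4 and attends on Day 7 is someone 7.3.4 wants to keep, yet cannot complete a survey within 4 hours of a dose. One site might take the survey and log a deviation; another might skip it. Section 10.1.5 does not settle this, because it concerns the visit-day window and not the time since dosing.

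The survey very likely carries the primary endpoint, although this is an inference. Section 9.6 lists only two questionnaires, 6.1 places the Early Outcomes Survey at Visit 3, and the visible Visit 3 items in 10.1.3 are concomitant medication, the adverse event query and "Dosing diary review by dedicated team member".

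If the score is not taken, 12.6.1 fills nothing in. The paired t-test, the only test named in the visible text, then uses only subjects who have a Day 7 value. With one open-label arm, no control group offsets selective loss. If those without a score do worse than the rest, the mean improvement is overstated for the FAS.

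**Working it through.** **1. The plan's own figure.** Inputs from 12.3: n = 75, difference 8.194, SD of differences 25, paired t-test, two-sided 5%. The noncentrality is 8.194 / (25/√75) = 2.84, which gives power of 79.997%. Then 75 / (1 − 0.25) = 100. Both stated figures reproduce.

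**2. Who is affected.** The timing rule touches only subjects who have stopped drops but still attend on Day 7. The documents give no rate for this. The 10% in 7.3.5 concerns people who do not come back, for whom survey wording can recover nothing. The 25% in 12.3 is a sizing allowance with no time point. I therefore assume 3% and 5% for the off-drop share, and show 10% and 25% as outer cases.

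**3. Shift in the mean.** Assume subjects on drops average −8.194 (SD 25), a fraction f is off drops, and those subjects do not change. With 100 treated, the FAS mean is (1 − f) × (−8.194), so leaving them out overstates the improvement by f × 8.194.

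| f | FAS mean | Overstatement if left out |
|---|---|---|
| 3% | −7.95 | 0.25 |
| 5% | −7.78 | 0.41 |
| 10% | −7.37 | 0.82 |
| 25% | −6.15 | 2.05 |

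**4. Effect on the test.** Let f now be the share with no Day 7 score for any reason. "Zero" sets those changes to 0 without spread. "+5" gives them a mean worsening of 5 points with SD 25. The tipping value is the single imputed change at which p reaches 0.05.

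| f | t, scored subjects only | t, zero | t, +5 (p) | Tipping value |
|---|---|---|---|---|
| 10% | −3.11 (n = 90) | −3.09 | −2.73 (0.008) | +23.1 |
| 25% | −2.84 (n = 75) | −2.81 | −1.92 (0.058) | +6.7 |

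For the last row under +5, the mean is (75 × −8.194 + 25 × 5)/100 = −4.90. With SD 25.53, t = −4.90/2.553 = −1.92.

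**5. False-positive rate.** Suppose the true FAS mean is zero and leavers are g points worse than stayers. Stayers then average −f × g, and the t-test on stayers (SD 25) rejects as follows.

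| f | g = 10 | g = 20 |
|---|---|---|
| 3% | 5.2% | 5.6% |
| 5% | 5.4% | 6.7% |
| 10% | 6.6% | 11.7% |
| 25% | 13.7% | 40.1% |

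The large values need the whole 25% allowance to be used up by Day 7, together with a gap that has no source in the documents.

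**6. The passages side by side.** The survey window is a scheduling instruction. No visible text makes it a condition for a score to be valid. Section 7.3.4 asks for follow-up and data after treatment stops, and 8.4 continues assessments after a deviation. The FAS definition keeps the subject, and the Per Protocol Set is where a timing deviation that affects efficacy would be handled. A survey taken off drops is observed data, so 12.6.1 does not reach it.

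**The case for a change.** The strongest reply is that no analysis rule can recover a survey that a site never took. Footnote [5] is what site staff read on the day, and taken literally it has no slot for a subject off drops. A sentence of clarification would cost little: no new visits, no change to the primary test, and one amendment through the IRB. A tipping-point analysis in the statistical analysis plan would be cheap as well.

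Part of this stands. The visible wording is incomplete, and a site could misread it. But the reading that skips the survey requires the timing rule to override 7.3.4 and 8.4, and no text gives it that priority. Staff following those two sections would take the survey and record the timing as a deviation. On the sensitivity analyses, the primary analysis text and the statistical analysis plan to which 12.6.1 defers cannot be seen, so their absence cannot be claimed. They would also leave the primary test as it is. Zero imputation hardly moves the result even at 25%. The tipping value of +6.7 and the p-value of 0.058 do show fragility at that level, but the 25% is a general dropout ceiling and would not be lowered by clearer survey wording.

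**Conclusion.** The concern does not call for a change. The literal gap between 6.1 with footnote [5] and 7.3.4 is real, but it is one that sites and analysts would fill sensibly from 7.3.4, 8.4 and the FAS definition: take the survey, note the timing, keep the score. Whether a score taken off drops counts is a question of how stopping treatment is handled, which the no-imputation sentence does not decide.

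The plausible size is 0.25 to 0.41 points if 3% to 5% are off drops at Day 7 with no change, and 0.82 points at 10%, against a detectable difference of 8.194. At 10% without a score, significance is lost only if the missing changes are set to about +23 points or worse. The 25% case is fragile under pessimistic assumptions, but it describes general dropout.

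This rests on assumptions that the documents do not confirm: the off-drop shares, the change among those subjects, the Early Outcomes Survey as source of the severity score, and the FAS as the primary analysis set (the visible text ties the FAS by name only to adverse event summaries). What the redacted analysis text says on missing or off-drop Day 7 scores cannot be judged from here.
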